9.3. Demographic and Baseline Characteristics

The demographic and baseline characteristics will be summarized. The list of characteristics that will be summarized include but are not limited to the following:

- Gender
 - Age (years) (#)
 - Age group 1 (<65 years, ≥65 years)
 - Age group 2 (3 groups: (<65 years, 65≤ - <75, 75≤ years)
 - Race (White, Black, Asian, American Indian or Alaska Native, Native Hawaiian or Other Pacific Islander, Not Collectable, Other)
 - Race Group (White, Asian, Other)
 - Ethnicity (Hispanic or Latino, Not Hispanic or Latino, Not Collectable, Unknown)
 - Region 1 (Japan, Rest of the World 1)
 - Region 2 (US, EU, Japan)
 - Region 3 (US, Rest of the World 3)
 - ECOG status at baseline (0, 1)
 - Height (cm) (#)
 - Weight (kg) (#)
 - BSA (m²) (#)
 - BSA (m²) by Region 2 (#)
 - Renal function at baseline (Normal/Mild/Moderate based on Cockcroft-Gault formula)
- (#) indicates a continuous variable to be summarized.

9.4. Subject Inclusion and Exclusion Criteria

Information regarding subject's inclusion and exclusion criteria will be listed on an individual subject basis.

Patients who were randomized but have not met all inclusion and/or exclusion criteria will be identified and summarized by treatment arm and inclusion/exclusion criteria that were not met.

9.5. Medical History

Significant medical history will be summarized for the AT population. The patients are summarized using counts and percentages. All medical histories will be coded using MedDRA version 16.1 (or greater) and summaries will use the system organ class and preferred term codes, as appropriate.

9.5.1. Cancer Medical History

- Primary Cancer Type (gastric, gastroesophageal (GE) junction, both)
- Tumor Grade (Well Differentiated, Moderately Differentiated, Poorly Differentiated, Unknown or Missing)
- Histology subtype (intestinal, diffused, mixed, unknown or N/A)
- Location of Primary Tumor
- Previous gastrectomy (Yes, No)
- Time from Initial Diagnosis to Randomization (months)
- Time from Confirmed Metastasis to Randomization (months)
- Number of prior regimens (<2, 2, 3, 4≤)
- Prior Treatment with Fluoropyrimidine (Yes, No)
- Prior Treatment with Platinum (Yes, No)
- Prior Treatment with Irinotecan (Yes, No)
- Prior Treatment with Taxane (Yes, No)
- Prior Treatment with Ramucirumab (Yes, No)
- Measurable disease (Yes, No)
- Number of metastatic sites (1-2, ≥3)
- Presence of liver metastases (Yes, No)
- Presence of lung metastases (Yes, No)
- Presence of peritoneal metastases (Yes, No)
- HER2 status

9.5.2. Non-Cancer Medical History

Non-cancer-related medical history will be presented as it is described in the beginning of the [Section 9.5](#).

9.6. Prior, Concomitant, and Survival Follow-up Medications and Therapies

9.6.1. Prior Anti-Cancer Therapies

Prior anti-cancer therapies will be summarized for the AT population and will include the following:

- Number of prior regimens (<2, 2, 3, 4≤)
- Prior therapies (fluoropyrimidine, platinum, taxane, irinotecan, ramucirumab, immunotherapy (PD1/PDL1) containing regimens, HER2i).
- Prior Treatment with Ramucirumab (Yes, No)
- Prior Treatment with Irinotecan (Yes, No)
- Prior Treatment with Taxane (Yes, No)
- Prior Treatment with Fluoropyrimidine (Yes, No)
- Prior Treatment with Platinum (Yes, No)
- Prior Treatment with HER2i
- Prior Treatment with Immunotherapy (PD1/PDL1) (Yes, No)
- Prior surgery (Yes, No)
- Previous gastrectomy (Yes, No)
- Prior Radiotherapy (Yes, No)

9.6.2. Prior and Concomitant Medications

Prior and concomitant medications will be summarized for the AT population. The patients are summarized using counts and percentages. All concomitant medications and therapies will be coded using WhoDDE (September 2015) and summaries will use the system organ class and preferred term codes, as appropriate.

All medications, prescription and over-the-counter, from the time of signed ICF through the 30-day Safety Follow-Up Visit, will be collected and summarized in the tables. This will include any medication used to treat AEs or SAEs during the safety follow-up period. Summarization will be performed separately for prior and concomitant medications (two different tables).

9.6.3. Non-study Systemic Anti-cancer Treatment during Survival Follow-up Period

Patients receiving non-study systemic anti-cancer treatments initiated during the follow-up period will be summarized in a table by treatment arm. The table will display the number and type of new non-study systemic anti-cancer treatments. The time to start of the new anti-cancer treatment will be presented as a listing and is defined as the start date of the new anti-cancer therapy minus the date of last dose of study medication + 1. If the start date of the new anti-cancer treatment is missing, the time to start of anti-cancer therapy will be missing for that patient.

9.7. Exposure to Study Medication

Exposure will be summarized and tabulated for the AT population. Study drug administration for number of cycles initiated will be summarized by cycle and overall for each treatment group. Dose level by cycle will be summarized for each treatment group. Patients with at least one dose reduction and first cycle with target dose reduction will be summarized for each treatment group. The number of delays in cycle initiation ≥ 8 days and the 1st delay ≥ 8 days will be summarized by cycle and overall for each treatment group. The number of delays in cycle initiation of ≥ 4 days will also be presented. Duration of cycles (excluding last cycle) will be summarized by cycle and overall for each treatment group. The number of patients that received $\geq 90\%$ of cycle 1 target dose, received $\geq 80\%$ of cycle 1 target dose will be summarized for cycle 1, cycles > 1 and entire study for each treatment group. Patients receiving more than 100% of the cycle 1 target dose or the current cycle dose will be summarized in interval categories of 20% (e.g. $>100\%$ to 120%, $>120\%$ to 140%, etc.) The total dose administered (mg/m^2), dose intensity ($\text{mg}/\text{m}^2/\text{wk}$), relative dose intensity (ratio to planned) will be summarized.

9.8. Duration of Survival Follow-up

A summary table showing the duration of follow-up will be presented by treatment arm for the ITT and AT population. The follow-up period for the purpose of this analysis is defined as the time starting on the date randomized until the last day of contact, or the day of withdrawal from study or the day of death, whichever occurs last (note, this definition of the survival follow – up period is different from one used in the Study Protocol). It will be summarized using the reverse Kaplan-Meier method (deaths are censored, censored subjects constitute events at the censored time) [22].

10. EFFICACY ANALYSES

This Section contains instructions how the efficacy analysis of the collected data will be performed and presented. As a general rule (unless otherwise is stated) efficacy analysis will use values of stratification factors collected on IXRS.

Assignment of the tumor assessments to the appropriate cycle will be performed according to the instructions displayed in CCI [REDACTED]. Additionally, if multiple tumor assessments are reported at an analysis time window (refer to Section 8.7 CCI [REDACTED]), then the logic described in Section 8.8 and specific data handling rules presented in CCI [REDACTED] will be applied.

10.1. Statement of the Null and Alternate Hypotheses

The null and alternate hypotheses are read as follows:

1. H_0 : active treatment does not have a differential effect on the primary assessment of mortality risk (OS HR). The null hypothesis presumes that no statistically significant difference in overall survival (OS) between two groups of subjects (investigational drug and placebo-controlled) is observed in the study.
2. H_A : active treatment does have a differential effect on the primary assessment of mortality risk (OS HR). The alternate hypothesis presumes that there is a statistically significant difference in overall survival (OS) between two groups of subjects (investigational drug and placebo-controlled).

CCI [REDACTED]

CCI

10.3. Multiple Comparisons and Multiplicity

To account for the multiplicity of the primary efficacy endpoint comparisons (one interim and one final analysis), the Lan-DeMets alpha-spending approach will be used with O'Brien-Fleming stopping boundaries to guide the efficacy evaluation at the interim and final OS analysis (see Section 12 for details).

All secondary endpoints comparisons will be made at the 2-sided 0.05 significance level. Since PFS is the only key secondary endpoint for regulatory registration purposes, no further multiplicity adjustments will be made. Assuming that OS demonstrates significance, the same criteria will be used for the analysis of PFS.

10.4. Analysis of the Primary Efficacy Endpoint

10.4.1. Primary Efficacy Analysis

OS in the ITT population will be compared between the 2 treatment groups (ITT population) using the stratified log-rank test (based on PROC LIFETEST, CCI  ). One- and 2-sided p-values will be presented. The study will be declared to have met its primary objective if the 1-sided p-value is be less than 0.0215 (please refer to [Section 12](#) for more details). The estimate of the hazard ratio (HR) and corresponding 95% CI will be provided using a Cox proportional hazards (CPH) model including treatment and the 3 stratifications factors in the model. Survival for each arm will be summarized using Kaplan Meier curves and further characterized in terms of the median and survival probability at 3, 6, 9 and 12 months, along with the corresponding 2-sided 95% CI for the estimates. The stratification factors will be populated as per the IXRS assignment.

Confidence intervals for median survival are based upon the methods of Brookmeyer and Crowley [16]. Confidence intervals for survivorship estimates are calculated using the log-log transformation [17] where the estimated variance of $\log(-\log(\hat{S}(t)))$ is:

$$\tau^2(t) = \sigma^2[\hat{S}(t)] / [\hat{S}(t)\log(\hat{S}(t))]^2 .$$

The 100 x (1- α)% confidence interval for $S(t)$ is given by:

$$[\hat{S}(t)]^{\exp(z_{\alpha/2}\tau(t))} \leq S(t) \leq [\hat{S}(t)]^{\exp(-z_{\alpha/2}\tau(t))}$$

CCI

10.4.2.1. Tests

The unstratified log-rank test and a CPH model (only treatment effect included in the model).

10.4.2.2. Potential Prognostic/Predictive Factors

Multivariate analysis using the CPH model, including the 3 stratification factors (as per IXRS) and potential prognostic/predictive factors: age group 1 (<65, \geq 65 years), race group (White, Asian, Other), gender, number of prior regimens (\leq 2, 3+), prior therapy (taxane yes or no, irinotecan yes or no), previous gastrectomy, gastroesophageal (GE) junction involvement, presence of peritoneal metastases, presence of liver metastases, presence of lung metastases, number of metastatic sites (1-2, 3+), time from confirmed metastases to randomization , measurable disease (yes, no), histology subtype (diffuse, intestinal), and HER2 status at the baseline.

10.4.2.2.1. Selection Process

Factors included in the model (please refer to [Section 10.4.2.2](#)) will be assessed for co-linearity and a stepwise selection process will be applied to identify a final subset of prognostic/predictive factors in the model. Once the subset has been established (retaining factors significant at the 10% level), treatment will be added to the final model to assess its effect in the presence of the identified covariates.

CCI

CCI

10.4.3. Key Secondary Efficacy Analysis

PFS will be analyzed with the methodology specified in [Section 10.4.1](#), [Section 10.4.2.1](#), [Section 10.4.2.2.1](#), and [Section 10.4.2.2.2](#). Comparisons will be made at the 2-sided 0.05 significance level. In line with FDA guidance (Clinical Trial Endpoints for the Approval of Cancer Drugs and Biologics) CCI

The list of other planned examinations reads as follows:

- Analysis that includes clinical progression as a PFS event in addition to the presence of radiological evidence of progression.
- Analysis including clinical progression as a PFS event that also counts initiation of non-study antitumor therapy as an event date rather than as date used to sensor subsequent response assessment.
- Analysis that includes all deaths and response assessments (without censoring missed visits) and counts as an event any one of the following list: radiological evidence of progression, clinical progression, initiation of non-study antitumor therapy, and death through the date of cut-off for survival.
- Analysis of time to first, second and third radiological tumor assessments from the date of randomization (Kaplan-Meier curves of times will be depicted and the corresponding supporting tables will be created; log-rank test will be applied for examination and comparison of the two groups).
- Analysis described above will also be run excluding high accrual (>25 patients) CCI

10.4.4. Other Secondary Efficacy Analysis

All other secondary endpoints comparisons will be made at the 2-sided 0.05 significance level.

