10.4.4.4. Quality of Life

Analysis of the EORTC QLQ-30 and QLQ-STO22 questionnaire should follow the instructions described in the manual created by the developers of the questionnaire. The manual SCManualQLQ-C30 can be found on the EORTC site <http://www.eortc.be/qol/files>. Note that the document contains SAS programs for correct calculation of scoring.

The QLQ-30 is composed of both multi-item scales and single-item measures. These include five functional scales, three symptom scales, a global health status / QoL scale, and six single items. Each of the multi-item scales includes a different set of items - no item occurs in more than one scale. The QLQ-STO22 is composed of 5 multi-item scales and 4 single-item measures.

Assignment of the QoL test to the appropriate cycle will be performed according to the instructions displayed in CCI. Additionally, if multiple QoL tests are reported at an analysis time window (refer to [Section 8.7](#) CCI), then the logic described in [Section 8.8](#) and specific data handling rules presented in CCI will be applied.

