10.4.4.4.5. Deterioration vs Stable Proportion

For each EORTC QLQ-C30 and QLQ-STO22 score, deterioration in QoL will be defined as a decrease in the score from baseline level of at least five points, the threshold proposed by Osoba et al. [21] as a small but meaningful change in QoL. For each EORTC QLQ-30 and QLQ-STO22 measure, the proportion of patients with deteriorating and (stable or improving) scores at weeks 4, 8 and 12 will be compared using Fisher's exact test. The results will be summarized as a separate table.

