10.4.4.4.6. Time to Deterioration – Main Analysis

Time to first deterioration in QoL (refer to [Section 10.4.4.4.5](#) for definition) will be evaluated for each arm using Kaplan-Meier estimates and compared using the log-rank test (and Cox proportional hazards models adjusting for the baseline value of the EORTC QLQ-C30 and QLQ-STO22 score, country and primary tumour type). Patients with no deterioration in EORTC QLQ-C30 and QLQ-STO22 scores will be censored at the end of study, cut-off date or death date.

CCI

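### Response, ECOG and QoL comparisons are each made at 2-sided 0.05 with no gate, no multiplicity control and no nominal label, so a trial that fails on OS could still call them significant

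*SAP*

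**What the plan says.** SAP 10.3 sets one rule for the whole secondary tier: "All secondary endpoints comparisons will be made at the 2-sided 0.05 significance level". It then closes the matter: "Since PFS is the only key secondary endpoint for regulatory registration purposes, no further multiplicity adjustments will be made". The only ordering it gives is between OS and PFS: "Assuming that OS demonstrates significance, the same criteria will be used for the analysis of PFS". Protocol 13.3.2.3 carries the same rule, again with PFS alone conditional on OS. SAP 10.4.4 repeats the level for the lower tier, "All other secondary endpoints comparisons will be made at the 2-sided 0.05 significance level", and mentions neither OS nor PFS.

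That lower tier has four endpoints (SAP 3.2.3): ORR, DCR, time to ECOG 2 or higher, and QoL. For QoL, SAP 10.4.4.4 lists five functional scales, three symptom scales, one global scale and six single items in the QLQ-C30. For the gastric module it says "The QLQ-STO22 is composed of 5 multi-item scales and 4 single-item measures".

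SAP 10.4.4.4.5 compares the proportion deteriorating on every measure by Fisher's exact test: "scores at weeks 4, 8 and 12 will be compared using" that test. SAP 10.4.4.4.6 adds time to first deterioration, "compared using the log-rank test (and Cox proportional hazards models" with covariates). Its heading calls this the main analysis, but the visible text names no scale as the main one.

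**The concern.** The ranking works backwards. PFS, the higher-ranked endpoint, may be tested only if OS succeeds, while the four endpoints below it may be tested whatever happens to OS and PFS. Read literally, a trial that fails on OS, and so cannot test PFS, can still report ORR, DCR, ECOG deterioration or a QoL scale as significant at 0.05.

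QoL is where this matters most, because the number of tests is large and the visible text gives no scale priority. A statement that QoL was maintained, or that it worsened, could rest on whichever of the 24 measures crossed 0.05 by chance.

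Such a statement is plausible. SAP section 3 says the analysis plan is meant to support a marketing application. Protocol 6.2.3 already reads a statistically significant ECOG result from the earlier colorectal trial as a sign that quality of life was preserved.

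**Working it through.** The documents state no error rate for the endpoints below PFS, so there is no plan figure to reproduce. The OS event target is not involved.

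**Counts, from SAP 10.4.4.4 to 10.4.4.4.6**

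- QLQ-C30: 5 + 3 + 1 + 6 = 15 measures.
- QLQ-STO22: 5 + 4 = 9 measures.
- Total: 15 + 9 = 24 measures.
- Fisher tests: 24 × 3 time points = 72.
- Log-rank tests: 24 × 1 = 24.
- Total: 72 + 24 = 96 tests.

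The Cox models are left out. Each repeats the log-rank comparison on the same data with covariates.

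**Expected false positives with no QoL effect**

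This is the number of tests × 0.05, and correlation does not change it.

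- 24 log-rank tests: 24 × 0.05 = 1.2.
- All 96 tests: 96 × 0.05 = 4.8 at most, since Fisher's test is conservative.

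**At least one p<0.05, independent tests**

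Either direction: 1 − 0.95^m. Favouring TAS-102 only: 1 − 0.975^m.

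- m = 24: 1 − 0.95^24 = 71%; 1 − 0.975^24 = 46%.
- m = 96: 1 − 0.95^96 = 99%; 1 − 0.975^96 = 91%.

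**At least one p<0.05, correlated tests**

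The documents give no correlations, so these are assumed. For m = 24 equicorrelated normal statistics with correlation ρ, the chance in either direction is 1 − ∫ φ(u) [Φ((1.96 − √ρ u)/√(1−ρ)) − Φ((−1.96 − √ρ u)/√(1−ρ))]^24 du. For results favouring TAS-102 only, the second Φ term is dropped. For the 96 tests, normal statistics were simulated with correlation ρ between measures and 0.3 to 0.7 between the four tests of one measure.

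| ρ between measures | 24 log-rank, either direction | 24 log-rank, favouring TAS-102 | 96 tests, either direction | 96 tests, favouring TAS-102 |
|---|---|---|---|---|
| 0 | 71% | 46% | 96–99% | 80–91% |
| 0.5 | 46% | 23% | 81–90% | 44–57% |
| 0.7 | 31% | 16% | 64–75% | 32–43% |
| 0.8 | 24% | 12% | 51–64% | 26–34% |

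The upper ends of the 96-test ranges at ρ = 0 are the fully independent case.

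**Check with the actual tests**

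A patient-level simulation under no effect ran the Fisher and log-rank tests themselves. It assumed 333 versus 167 patients, 35% deteriorating, and 80%, 50% and 35% completing at the three time points. The chance of at least one p<0.05 across the 96 tests was 96%, 94% and 87% at latent between-measure correlations of 0.2, 0.4 and 0.6. The expected number of false positives was 4.1 to 4.3.

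**The case against.** The best defence is that this is a deliberate, disclosed and pre-specified choice. OS is protected by alpha spending and PFS by the gate on OS. The remaining endpoints are ranked separately as other secondary endpoints, and the plan gives its reason for not adjusting them. Testing supportive endpoints at a per-comparison level is a common convention, and the QoL time points were fixed in advance on expected compliance (protocol 13.3.2.3). All of that stands. It shows that confirmatory error is intact, but it does not explain why the supportive comparisons carry a significance level without being called nominal or descriptive.

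A reader might infer more than the documents support:

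- **That the sponsor intends to claim a QoL benefit if OS fails.** No passage says so. The text permits such a statement; it does not plan one.
- **That there are 120 QoL tests.** Adding 24 Cox models to the 96 gives that figure, but it counts one comparison twice.
- **That a chance QoL finding is likely however the tests are counted.** Across all 96 tests the chance exceeds one half at every correlation tried. For the 24 log-rank tests it is below one half at correlations of 0.5 and above. Scales completed by the same patients at the same visit are unlikely to be independent, so 71% is an upper figure. For results favouring TAS-102 the chance is lower again.
- **That no main QoL measure exists anywhere in the plan.** SAP 10.2, text after 10.4.4.4.6 and the appendices are redacted, so this can be said only of the visible text. SAP 10.3, where the multiplicity rule sits, is visible.

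**Conclusion.** The point holds as a gap in what may be called significant; the OS and PFS tests themselves are sound. SAP 10.3, SAP 10.4.4 and protocol 13.3.2.3 together let ORR, DCR, ECOG deterioration and 24 QoL measures be called significant at 2-sided 0.05 whatever the OS and PFS results.

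For QoL with no true effect, at least one chance result in either direction has a probability of about 51% to 99% over the 96 tests, and of 24% to 71% over the 24 log-rank tests. For results favouring TAS-102, the 24-test figure runs from 12% to 46%. These ranges rest on assumed between-measure correlations of 0.8 down to 0, and the 96-test range also on the assumed correlation between tests of the same measure. Even the smallest figure is more than four times the 2.5% that a single test would allow in that direction (12 / 2.5 = 4.8). This is a cheap improvement worth making, because it changes what the trial may conclude.

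**What to change.** In SAP 10.3 and 10.4.4, state that ORR, DCR, time to ECOG 2 or higher and QoL carry a significance statement only if OS and then PFS are significant. Name one QoL comparison as the main one, for example time to deterioration of QLQ-C30 global health status. Report every other QoL p-value as nominal, with the estimate and 95% CI. Because protocol 13.3.2.3 holds the same rule, record the departure in SAP section 14 or by amendment, so that the two documents do not disagree silently.

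The gate stops claims from a failed trial. It does not by itself control error among the four endpoints once OS and PFS have succeeded: with one QoL test, the chance of at least one false positive is 1 − 0.95^4 = 19% if they are independent and none has an effect. If control there is wanted, test the four in a fixed order, or each at 0.05 / 4 = 0.0125. Holm across the 24 time-to-deterioration tests is also optional.

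The cost is wording and table footnotes, with no new data or analyses and no change to the OS or PFS tests. The downside is that fewer secondary results can be called significant.

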10.4.4.1. ORR

Overall response rate (ORR) is defined as the proportion of patients with objective evidence of CR or PR. The treatment comparison for ORR will be based on the TR population using Fisher's exact test in the subset of patients in the Intent-to-treat population with measurable disease at baseline (TR population). Treatment estimates and differences will be presented along with the associated 2-sided 95% CIs constructed using the Clopper-Pearson approximation to the exact binomial proportion [17] for individual estimates within group; and the normal approximation for the difference between groups.

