13.2.3. Other Secondary Efficacy Endpoints

13.2.3.1. Overall Response Rate (ORR)

The assessment of ORR will be based on Investigator review of the images. ORR is defined as the proportion of patients with objective evidence of CR or PR.

At the analysis stage, the best overall response will be assigned for each patient as the best response recorded from all responses recorded after study randomization. If applicable, responses recorded after disease progression or initiation of non-study cancer treatment will be excluded. A patient's best response assignment of SD needs to be maintained for at least 6 weeks after study randomization. Per RECIST 1.1, responses of PR or CR in studies with survival as the primary endpoint do not have a minimum time requirement to maintain the response. ¹²

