13.3.2.3. Secondary Endpoint Analyses

All secondary endpoints comparisons will be made at the 2-sided 0.05 significance level. Since PFS is the only key secondary endpoint for regulatory registration purposes, no further multiplicity adjustments will be made. Assuming that OS demonstrates significance at the 1-sided 0.025 level, PFS can subsequently be tested at the 2-sided 0.05 level.

PFS

PFS will be analyzed with the methodology specified in Section 13.3.2.1 and Section 13.3.2.2a, c, and d. CCI

ORR and DCR

The treatment comparison for ORR and DCR will be based on the TR population using Fisher's exact test. Treatment estimates and differences will be presented along with the associated 95% CIs.

Time to Deterioration of ECOG Performance Status

Time to deterioration of ECOG performance status to a score of 2 or higher will be analyzed using methodology described in Section 13.3.2.1. Patients not reaching an ECOG of 2 or more (3, 4 or 5) will be censored at the last recorded ECOG assessment.

Quality of Life

Questionnaire compliance rates, for both scales, will be assessed at each measurement time point (baseline, prior to cycle 2, 3, 4, etc.).

Descriptive statistics, for both scales, for the summary scores, as well as the subscale scores will be provided for each assessed time point. In addition, change in QoL scores at representative time points will be determined for the summary, all domains and single items by subtracting each patient's score from their corresponding baseline score. Representative time points will be prior to cycle 2, 3 and 4, chosen based on expected patient compliance to be adequate to allow meaningful analyses, considering the expected treatment duration in the two study groups.

For each domain, the proportion of patients with deteriorating, stable or improving scores prior to cycles 2, 3 and 4 will be compared using Fisher's exact test. In addition, time to QoL deterioration will be evaluated for each arm using Kaplan-Meier estimates and compared using the log-rank test. The criteria for deteriorating, stable or improving scores will be detailed in the SAP.

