3.2.3.1. Overall Response Rate

The assessment of ORR will be based on Investigator review of radiologic images and following RECIST criteria (version 1.1 2009). ORR is defined as the proportion of patients with objective evidence of CR or PR. The primary assessment of ORR will be in the ITT population, restricted to patients with measurable disease (at least 1 target lesion) at Baseline.

At the analysis stage, the best overall response will be assigned for each patient as the best response recorded from all responses recorded from the start of treatment through the treatment period (excludes assessments during follow-up). If applicable, responses recorded after radiologic disease progression or initiation of non-study antitumor therapy will be excluded. A patient's best response assignment of SD needs to be maintained for at least 6 weeks from the start of treatment.

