3.2.3.2. Disease Control Rate

DCR is defined as the proportion of patients with objective evidence of CR, PR, or SD (stable disease). The assessment of DCR will parallel that of ORR.

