7.3. Tumor Response(TR) Population

The “Tumor Response (TR) Population” will include all patients in the ITT population that meet both of the two following criteria:

1. Subject has measurable disease (at least one target lesion) at baseline;
2. Subject has at least one post-baseline evaluation or early disease progression/cancer-related death occurred before first evaluation on treatment (post-baseline) took place.

All analyses using this population will be based on the treatment assigned by IXRS.

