10.4.4.2. DCR

Disease control rate (DCR) will be analyzed using the same methodology as that for ORR.

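### For ORR and DCR the SAP makes one patient set primary but tests in another that is defined inconsistently, and its best-response window differs from that in the protocol's statistics section

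*SAP*

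**What the plan says.** **Analysis set.** SAP 3.2.3.1: "The primary assessment of ORR will be in the ITT population, restricted to patients with measurable disease (at least 1 target lesion) at Baseline". SAP 3.2.3.2 adds: "The assessment of DCR will parallel that of ORR".

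The sections on the treatment comparison name a different set. Protocol 13.3.2.3: "The treatment comparison for ORR and DCR will be based on the TR population". SAP 10.4.4.1: "The treatment comparison for ORR will be based on the TR population". Later in the same sentence, the SAP describes where the Fisher test is run: "in the subset of patients in the Intent-to-treat population with measurable disease at baseline (TR population". SAP 10.4.4.2: "Disease control rate (DCR) will be analyzed using the same methodology as that for ORR".

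**Definition of TR.** SAP 7.3 requires measurable disease at baseline and a second condition: "Subject has at least one post-baseline evaluation or early disease progression/cancer-related death occurred before first evaluation on treatment (post-baseline) took place". The protocol synopsis, Protocol 13.1 and the SAP synopsis instead ask for a tumor evaluation made during treatment, with the same exception for early progression or cancer-related death.

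**Best-response window.** Protocol 13.2.3.1 takes the "best response recorded from all responses recorded after study randomization", leaving out those after progression or new cancer treatment. SAP 3.2.3.1 limits the window to the treatment period and expressly leaves out follow-up assessments. Protocol 11.4 also stops at the end of treatment.

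**The concern.** A programmer cannot satisfy all of these passages at once. A patient with measurable disease who withdraws, stops for toxicity, dies of a non-cancer cause or is never dosed, all before any scan, is in the SAP 3.2.3.1 denominator as a failure. The same patient is absent from TR as SAP 7.3 defines it. SAP 10.4.4.1 carries both ideas in one sentence: it names TR and then describes the SAP 3.2.3.1 set.

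The window affects the numerator. Patients who stop without radiologic progression continue to be scanned every 8 weeks (Protocol 8.6, 10.1.13 and 10.2.8), so a first PR or SD seen off treatment counts under Protocol 13.2.3.1 and not under SAP 3.2.3.1.

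Two things are at stake. If the choice is left open, it could be made after the data are seen. And if TR is used as defined, the test conditions on a post-randomization event, which raises the rate more in the arm with more unevaluated patients.

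**Working it through.** The plan gives no power, rate or exclusion figure for ORR or DCR in this trial, so there is no stated figure to reproduce. Every input below is an assumption, apart from the 500 patients at 2:1 and the two-sided 0.05 level (SAP 10.4.4).

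**1. One arm, same data, different passages.** Assume 200 patients with measurable disease. Of these, 80 have disease control on treatment, 10 have their only scan in follow-up (5 of them SD), and 10 are never scanned. None of the last two groups has early progression or cancer-related death.

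| Set | Window | DCR |
|---|---|---|
| ITT measurable (SAP 3.2.3.1) | treatment period | 80/200 = 40.0% |
| TR, any post-baseline scan (SAP 7.3) | treatment period | 80/190 = 42.1% |
| TR, scan during treatment (Protocol 13.1, both synopses) | treatment period | 80/180 = 44.4% |
| ITT measurable | all after randomization (Protocol 13.2.3.1) | 85/200 = 42.5% |

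The step between the two TR definitions (2.3 points) is as large as the step from the ITT measurable set to TR under SAP 7.3 (2.1 points).

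**2. False-positive rate if TR is used.** If a share e of an arm is dropped and all of those dropped would have been failures, the TR rate is p/(1 − e). Assume 90% of 500 patients are measurable (300 v 150) and the true DCR is 40% in both arms. Rejection at two-sided 0.05 by Fisher's test was found by exact enumeration of two binomials. The last column uses the same denominators with 40% in both arms, which separates bias from the discreteness of Fisher's test.

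| Excluded, TAS-102 v placebo | n retained | TR rates | Spurious difference | Rejection | Same n, no bias |
|---|---|---|---|---|---|
| none | 300/150 | 40.0% v 40.0% | 0 | 4.26% | 4.26% |
| 10% v 10% | 270/135 | 44.44% v 44.44% | 0 | 4.38% | – |
| 3% v 1.5% | 291/148 | 41.24% v 40.61% | 0.63 points | 4.51% | 4.41% |
| 5% v 2.5% | 285/146 | 42.11% v 41.03% | 1.08 points | 4.95% | 4.56% |
| 10% v 5% | 270/142 | 44.44% v 42.11% | 2.34 points | 6.95% | 4.45% |

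Swapping the arms in the last row gives 6.72%. With ORR at 5% in both arms, the scenarios with no or unequal exclusion, in either direction, give rejection between 3.6% and 4.1%, and the largest spurious difference is 5.56% − 5.26%, about 0.3 points.

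**3. A single result can change.** With 5% v 20% excluded, a deliberately large imbalance, 135/300 v 52/150 (p = 0.042) becomes 135/285 v 52/120 (p = 0.51) with the same patients controlled. With equal 10% exclusion it becomes 135/270 v 52/135 (p = 0.034). For the window, one more off-treatment responder moves ORR from 12/300 v 1/150 (p = 0.069) to 13/300 v 1/150 (p = 0.042).

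**The case against.** **Every passage that assigns the treatment comparison to a set names TR.** SAP 3.2.3.1 speaks of a primary assessment and mentions no test. A reader might infer that the Fisher test itself is assigned outright to two different sets; the documents do not go that far. What stands is narrower. The SAP calls one set primary and compares arms in another, and SAP 10.4.4.1 describes TR in a way that SAP 7.3 does not allow.

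**Exclusions are probably few.** TR keeps early progression and cancer-related death, and Protocol 10.1.13 and 10.2.6 ask for every effort to scan patients who stop for other reasons. This stands. A reader might infer that TR favours TAS-102, or that the false-positive rate is materially inflated. Neither is supported: the documents give no exclusion rate by arm, so the direction is unknown, and in the working only the 10% v 5% scenario exceeds 5%.

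**Moving the test out of TR departs from Protocol 13.3.2.3.** This also stands. Keeping TR and correcting SAP 3.2.3.1 and the description in SAP 10.4.4.1 would remove the ambiguity too. The case for the ITT measurable set is that the SAP already labels it primary, that Protocol 13.1 makes ITT primary for all efficacy parameters, and that it avoids selecting patients on what happens after randomization.

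**The window has no clear winner.** Protocol 13.2.3.1 and SAP 3.2.3.1 are both worded as analysis-stage rules. The treatment-period window agrees with Protocol 11.4, but it ends at a post-randomization event. Either choice is defensible.

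**Redaction.** Some tumor-assessment handling rules and some SAP Section 14 entries are blacked out and may settle the operative rule. The visible entries do not, and the visible passages would still disagree.

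**Conclusion.** The conflict is real on the visible text, for the set, for the definition of TR and for the best-response window. It should be settled before unblinding, so that the ORR and DCR rates and p-values do not depend on which passage was followed.

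Its size is unknown and may be small. If exclusions are few or balanced, the effect on the tests is negligible (4.51% rejection against 4.41% without bias at 3% v 1.5%). It becomes visible for DCR when the arms differ by several points (6.95% against 4.45% at 10% v 5%), and is trivial for ORR at a 5% rate. These figures rest on assumed counts, rates and exclusions.

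A reader might infer that the trial's main conclusions are at risk. They are not: ORR and DCR are other secondary endpoints outside the OS-then-PFS sequence.

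**What to change.** Revise the SAP before database freeze, the deadline set in SAP Section 2, and log the change in SAP Section 14 as a stated departure from Protocol 13.3.2.3:

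1. Run the ORR and DCR Fisher tests primarily in ITT patients with measurable disease at baseline, as in SAP 3.2.3.1 and 3.2.3.2. Count patients with no post-baseline evaluation as non-responders and as not controlled.
2. In SAP 10.4.4.1, delete both references to the TR population.
3. Give TR one definition in the SAP synopsis and SAP 7.3, keep it as a sensitivity analysis, and tabulate exclusions by arm and reason.
4. Reconcile Protocol 13.2.3.1 with SAP 3.2.3.1 and Protocol 11.4 by naming one best-response window as primary and reporting the other as a sensitivity analysis.

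**Cost.** SAP wording, one exclusion table and two sensitivity analyses; no new data. For the same window, each arm's rate will be equal to or lower than in TR (40.0% against 42.1% in the illustration). The protocol text will still name TR unless it is amended, which under Protocol 15.1 means submission to the IRB/IEC and authorities; that is why the departure should be stated openly in the SAP.
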